12.0 RISK/BENEFIT RATIO	
13.0 REFERENCES	

1.0 Purpose

We have demonstrated that administration of HER-2/neu pulsed DC1 in patients with DCIS and early invasive breast cancer (IBC) results in strong immunologic responses as well as apparent clinical responses during 4 and 6 week neoadjuvant vaccination. Patients with locally advanced breast cancer that have significant nodal disease have significant risk of systemic recurrence. In addition, those patients with recurrence after chemotherapy and trastuzumab have significant risk of additional local or systemic recurrence and may be resistant to trastuzumab. Those patients with HER-2 2+ that are FISH negative that are often ER positive with significant nodal disease are also at high risk for recurrence despite chemotherapy and anti-estrogen therapy. These patients are not classically treated with trastuzumab but may still respond to HER-2 directed therapy but also have diminished immunity to HER-2. All these patients have little additional therapy options. We hypothesize that adding DC1 vaccines pulsed with HER-2, will reduce the risk of recurrence and diminish deaths in these high risk patients. The primary goals of this trial will be to determine the safety and immune activity of HER-2 pulsed DC1 vaccine in patients with high risk HER-2^{pos} breast cancer with significant risk of systemic recurrence. We will also explore the possibility of determining whether circulating tumor cells can be used as surrogate to assess response to vaccination.

2.0 Duration of Study

This study will enroll 18 evaluable subjects over 1.5 years averaging 10 subjects per year. Evaluable implies that a patient received all 6 vaccinations and underwent leukapheresis after the vaccinations for immune response evaluation.

Fifteen subjects were enrolled at the Rowan Breast Center. Approximately 4 subjects will receive their treatment at follow up at Moffitt Cancer Center while remaining subjects will continue to be followed at Rowan Breast Center.

3.0 Subject Recruitment

Women with advanced breast cancer with ≥ 4 or more positive nodes with classic HER-2^{pos} or HER-2 2+ FISH negative, or those with local or systemic recurrence that are rendered NED by any means will be recruited from the clinical practices of the Rena Rowan Breast Center at the Hospital of the University of Pennsylvania and the Breast Center Moffitt Cancer Center.

4.0 Location of the Trial

The subjects will be recruited and followed in the Rowan Breast Center and the Moffitt Cancer Center. Mammograms will be performed at either site. Leukapheresis will be performed in the Apheresis Infusion Blood Donation Center on the 3rd Floor of Ravdin and at Moffitt Cancer Center. Elutriation will be performed in the FDA approved facility in the Blood Bank on 3 Ravdin and at Moffitt Cancer Center. The vaccines will either be prepared in the FDA approved facility, under the direction of the Vaccine Production Facility in the M2GEN building on the McKinley campus at Moffitt Cancer Center under the direction of Vaccinations Version v2 03/01/2017

Pilot Phase I HER-2 Pulsed DC Vaccine to Prevent Recurrence for Patients with HER-2 Driven High Risk Invasive Breast Cancer will be administered in the Clinical Research Center 1 Dulles Building at Penn or at Moffitt Cancer Center..

5.0 Background

5.1 The Problem

Most breast cancer patients, especially those with high-risk HER-2 positive or triple negative breast cancers, live with significant fear of recurrence-even when initial therapy appears successful. Patients with positive lymph nodes or patients with locally advanced HER-2 positive or triple negative cancer treated with neoadjuvant therapy that have residual disease found at surgery, both have significant risk of systemic recurrence⁵. Tragically, there is little to offer these patients in the way of recurrence risk reduction that does not come with significant toxicity or other deleterious side-effects. Even those patients with intermediate expression of HER-2 (2+) are at significant risk for late recurrence⁶. In addition, solid evidence now suggests HER-2 expressing stem cells and disseminated tumor cells can be found in the marrow and metastatic deposits in patients whose primary tumor does not express significant HER-2⁷. Even amongst HER-2 negative patients EGFR (HER-1) or HER-3 pathways are active and phosphorylated HER-2 proteins are identified⁸. These numerous patient populations are therefore in great need of new therapies to prevent outgrowth of distant disease, provided physicians and scientists can develop technologies to eliminate these remaining dormant cancer stem cells that will ultimately reactivate, leading to significant mortality.

Role of Receptor Tyrosine Kinases in Breast Development and Tumorigenesis

To explain why these molecules are important in breast cancer development is to understand their role in normal breast development. These RTK molecules are critically involved in multiple levels of breast development ⁹. HER-1 and HER-2 are expressed in early breast bud development especially Her-1 (EGFR) which is required for duct elongation at puberty. HER-2 and HER-3 play particularly important roles in duct elongation and branching during pregnancy and invasion of mammary pads. Hence they are critically involved in normal breast development and lactation. Mutation or assault from carcinogens may cause these molecules to at later time become over-expressed or aberrantly expressed in breast tumor tissue. The expression of these molecules could be a particularly critical site for interactions with viruses, other pathogens, and chronic inflammation causing damage or mutation and over- expression of the HER members. There are examples of identified mutations in HER-1, HER-2 and HER-3 in all phenotypes of breast cancer ^{10, 11}.

Several murine models have been identified where over-expression of HER family members leads to invasive breast cancer development in mature mice¹². Over-expression of these molecules appears to be sufficient to cause breast cancer development. Evidence is fairly abundant in human tissues that these molecules are expressed in early human breast cancers. We have demonstrated that HER-2 expression in DCIS is associated with finding invasive disease suggesting HER-2 may be progression factor ^{13, 14}. HER-3 is also expressed in DCIS and we have found that its expression increases with grade of DCIS. HER-1 is least expressed in early breast cancer except in triple negative DCIS and few other instances. HER-1 is expressed in about 30% of the DCIS lesions in BRCA1 mutation carriers going along with its expression in triple negative breast cancer. Taken together these HER family members seem to play an important role in normal breast development and when mutated or over-expressed play a dominant role in early breast cancer development.

Immune Response Impacts Breast Cancer

Evidence has demonstrated that infiltration of breast tumors with CD8 T cells results in prolonged survival¹⁵. There is also evidence that accumulation of CD4 and CD8 T cells in regional nodes is associated with better outcomes as well¹⁶. Counteracting this there is an accumulation of macrophages, immature myeloid suppressor cells and regulatory T cells that inhibit the immune response and promote growth and invasion of tumor cells^{17, 18}. Chemotherapies such as cyclophosphamide and docetaxol may eliminate some of the inhibitory cells enhancing immune responses¹⁹. There is evidence that combinations of chemotherapy and immune therapies with antibodies may increase responses such as seen with trastuzumab²⁰. Adding immune therapies especially through vaccines with chemotherapy may enhance the immune response as the inhibitory cells are diminished thus filling the immune space with tumor specific lymphocytes. We will take advantage of chemotherapy to open space in the immune repertoire and vaccinating to add specific anti-HER T cells to eliminate residual microscopic tumor deposits.

5.2 The Solution

The HER family of RTK provide critical signaling for development of breast cancer. HER-1 (EGFR) HER-2 and HER-3 have all been shown critical in normal breast development as well as breast tumorigenesis and invasion⁸. These molecules are over-expressed or mutated in a significant fraction of early and late breast cancer lesions ^{13, 21}. These are particularly dominant in HER- 2 and triple negative breast cancers ²². There is evidence that therapeutic antibodies like trastuzumab and pertuzumab, combined with chemotherapy, can have dramatic impacts in eliminating these primary tumors²³. However, there is also evidence of the molecules being involved in resistance to treatments ²⁴. Patients with locally advanced HER-2/neu and triple-negative cancers are at significant risk of systemic recurrence, especially when complete pathologic response is not obtained with neoadjuvant chemotherapy. We believe that targeting these pathways with a cellular immune response (particularly CD4 T cells) may prevent or eliminate dormant tumor cells remaining after therapy. Our preliminary data outlined below highlights an opportunity to potentially increase complete responses and help prevent recurrence in these patients with significant risk of systemic failure following standard therapy. Dendritic cell cancer vaccines combined with chemotherapy may increase complete responses giving breast cancer specific immune cells greater opportunity to function while the immune repertoire is being shifted by chemotherapy to anti-breast cancer response and offer the chance to test secondary prevention of breast cancer in high risk settings. There is a need to determine whether this ICAIT DC1 can activate CD4 and CD8 T cells prior to or in combination with chemotherapy with or without added trastuzumab. This would be a tremendous opportunity to improve outcomes for these high risk patients.

5.3 Preliminary Data

Experience with the vaccine to prevent recurrence: DC1 induces durable Th1-polarized anti-HER-2 responses with apparent clinical activity. A large body of novel and well-founded preclinical and clinical data justifies and supports our expandable platform for breast cancer prevention. We have completed a phase-I clinical trial with 27 subjects to vaccinate against HER-2/neu over-expressing early breast cancer (Ductal carcinoma in situ-DCIS) or DCIS with microinvasion^{3,4}, and are currently undertaking a second phase I/II study to extend these findings.

Subjects diagnosed with HER-2/neu^{pos} DCIS were vaccinated four times at weekly intervals prior to scheduled surgical resection of the tumor. The vaccines consisted of HER-2 peptide-pulsed autologous DC specially activated with IFN- γ and a clinical-grade toll-like receptor agonist (LPS), resulting in high-level IL-12 and Th1 chemokine secretion (DC1). The peptides used to pulse ICAIT DC consisted of 6 HLA class II promiscuous binders, as well as two HLA class I binding peptides (for HLA-A2.1^{pos} subjects). A summary of trial results is shown in the composite Figure 1 A-G. Briefly, Immunohistochemical staining and comparison of pre-vaccine biopsy with post-vaccine surgical specimen showed that vaccination induced heavy influx of CD4^{pos} helper-T cells around DCIS (Fig. 1A) as well as CD8^{pos} CTL and CD20 B cell (not shown). Immunohistochemical staining of HER-2/neu expression by DCIS in the pre-vaccine biopsy ("PRE") compared with the post-vaccine surgical specimen ("POST") indicated marked reduction of HER-2 expression in half of the subjects (Fig. 1B). The left panels of "B" show photo microscopy of stained DCIS sections from one representative subject (note loss of brown HER-2 staining in "POST" specimen) while the right panels show composite data of HER-2 reductions from 8 sample subjects as well as unvaccinated controls. No such reductions were observed in an unvaccinated contemporaneous control group (Fig. 1B) suggesting that vaccination could eliminate HER-2-overexpressing tumor cells. A comparison of estimated tumor size determined radiographically prior to vaccination with the actual tumor removed during surgery indicated reductions in the area of disease for about half of the subjects, with results for five of these clinically-responsive individuals shown (Fig. 1C). In fact, five of 27 subjects had no detectable DCIS at the time of surgery, suggesting vaccine-induced elimination of DCIS for some cases. For HLA-A2.1^{pos} subjects, we routinely demonstrated the capacity of post-vaccination CD8^{pos} T cells to directly recognize and secrete IFN- γ in response to HER-2^{pos} breast cancer cell lines in vitro. Results from a representative subject are shown (Fig.1D). This is important since CD4^{pos} and CD8^{pos} T cell infiltration in IBC is associated with long-term survival. The immunity generated by this vaccination

regimen proved to be extremely long-lived. Seventeen of twenty-seven subjects voluntarily provided additional blood samples 8-48 months post-vaccination. All subjects showed long-term CD4 T cell immunity to vaccine peptides by ELISpot. Anti-peptide results for subjects 1, 2 and 6 (taken 48, 48 and 43 month's post-vaccination, respectively) without prior stimulation are shown (Fig. 1E). Note that the long-term recall responses to vaccine peptides are often superior in magnitude to the recall response against tetanus toxoid. Despite the fact that this vaccine regimen was not optimized for antibody induction, we nonetheless demonstrated in some patients' sera a vaccine-induced increase in complement-dependent lysis of HER-2/neu^{pos} tumor lines in vitro (Fig. 1F), a property not seen with trastuzumab. Although antibody titers appeared fairly low (not shown), these data provide strong encouragement that antibody responses are present and ripe for dramatic improvement. Of utmost importance in this completed trial and a second follow-on trial now in progress is that we have a composite complete pathologic response rate of about 35% in ER^{neg} HER-2^{pos} (i.e. hormoneindependent) DCIS patients compared with 4% for ER^{pos} HER-2^{neg} (Fig. 1G). Since pathologic CR in breast cancer is associated with decreased risk of recurrence and deaths, it is not surprising that we have observed no breast cancer events in the patients that are ER^{neg} HER-2^{pos} compared to the group that is ER^{pos} HER-2^{pos} (Fig. 1G) we are highly confident that this Th1-polarizing DC vaccine will be associated with diminished secondary recurrence of DCIS and IBC. We wish to determine whether these vaccines following chemotherapy can induce immune responses and ultimately decrease recurrence in high risk node positive patients.

Clinical experience with DC1 vaccines: The vaccines are readily produced from all 80 subjects thus treated with early breast cancer. There is abundant IL-12 production. There is 85-90% induction of CD4 and CD8 T cells that recognize HER-2 post vaccination. None of these patients had immediately had chemotherapy or trastuzumab. The side effects of vaccine included grade 1 and 2 fevers, chills, fatigue, injection site soreness, headache. There were <10% of patients with asymptomatic declines in MUGA scan all within normal range above 50%. There was no one that developed heart failure clinically or by cardiac ejection. Any grade 1 or 2 changes in cardiac ejection fraction were reverted to baseline in repeat scan 30 days later. Thus the vaccines were considered safe and well tolerated.

Evidence for CD4 T cells that recognize extracellular domain HER-1 and HER-3 in early breast cancer: The majority of DCIS patients even prior to vaccination have evidence of CD4 T cells that secrete INF- γ when stimulated with extracellular domain (ECD) HER-1 (Fig 2 left graph). Those patients that do not have anti-HER-1 response developed a response to HER-1 following vaccination against HER-2 (Fig 2 right graph). There were only a few patients with evidence of HER-3 CD4 T cell responses prior to vaccination but the majority developed suggestion of weak CD4 T cell responses beginning after vaccination (Fig 3). These data support that following HER-2 vaccination using DC1 there is evidence that immune responses against HER-1 and HER-3 can be generated and are ripe for the improvements proposed in this application.

iDC

Fig 2. Patients CD4 T cells pre and post vaccine were co-cultured with extracellular domain HER-1 pulsed immature DC for 10 days. After 10 days the T cells were tested against IDC pulsed with HER-1 or irrelevant antigen. Left graph represents patients with pre-existing HER-1 responses and right graph only post vaccine is CD4 T cell responses seen against HER-1.

Fig 3. (Below) Pre and post vaccine CD4 T cells were co-cultured with immature or DC1 pulsed with HER-3 for 10 days. After 10 days they were tested against immature DC pulsed with HER-3 or irrelevant protein. Typically both patients demonstrate post-vaccine HER-3 reactivity when cells were stimulated with only DC1.

Activation of DC1 in patients with IBC: Several patients that were enrolled on the prior Phase I/II DC1 vaccine trials ultimately were discovered to have invasive cancers from 5 mm to 1.6 cm. We were able to prepare DC1 activated with IFN- γ and LPS inducing highly functional DC (not shown). In addition we have been able to prepare DC1 from patient with locally advanced HER-2 expressing IBC following treatment with chemotherapy and trastuzumab (Fig 4). Both Immature and DC1 pulsed with ECD HER-3 were able to stimulate autologous CD4 T to specifically secrete IFN- γ when primed by DC1. There was no evidence of immune response to HER-2 or HER-1 that could be generated by DC1 *ex vivo*. These results have been observed in other patients with IBC and suggest these immune responses to HER-1 and HER-2 can be substantially improved with DC1 vaccines.

We have treated 70 patients with this vaccine with only grade 1 and 2 toxicities including expected fever, chill, fatigue, aches, injection site soreness, and grade 1 and 2 decrease in cardiac output all in normal range no abnormal ejections. Repeat 30 days later return to baseline this is about 10% decrease in about 10% of patients treated.

Role of Anti-HER-2 CD4 T cells in Breast Tumorigenesis: We have tested CD4 T cells from healthy donors, benign breast biopsy patients (not shown), HER-2 expressing DCIS patients and patients with HER-2 expressing IBC. There is a progressive loss of anti-HER-2 CD4 reactivity to HER-2 from DCIS through early Stage I breast cancer (Fig 5). Note healthy donors and benign breast biopsy patients have similar results. In addition, IBC patients treated with trastuzumab and chemotherapy do not regain anti-CD4 T cell reactivity to HER-2, but vaccinated Stage I HER-2 expressing patients treated with HER-2 pulsed DC1 vaccines do (Fig 6) suggesting that these vaccines may correct underlying immune defect in CD4 T cells against HER-2.

Patient status

Figure 5. Loss of anti-HER-2 CD4 Th1 response from Healthy donors to HER-2+ DCIS and near complete loss in HER-2 positive IBC

Figure 6. Chemotherapy and trastuzumab do not restore anti-HER-2 CD4 Th1 (A); DC1 Vaccines restore anti-HER-2 CD4 Th1(B); even matched for Stage I only DC1 vaccines restore immune response (C); Anti-HER-2 CD4 Th1 after activation with DC1 remain somewhat intact following chemotherapy (D,E).

6.0 Research Design

6.1 Consent Process

The PIs or their designees will be responsible for explaining all aspects of the initial informed consent to the subject. The person obtaining consent can have the subject sign the consent. The PI and protocol coordinator will review the data and deem the subject eligible. Once the consent is obtained the subject will be assigned a study number or identification.

6.2 Identification of subjects

Subjects with a diagnosis of standard HER-2/neu-positive IBC or HER-2 2+ but FISH negative with Stage IIIA \geq N2, or have recurrent HER-2 positive metastatic breast cancer rendered NED by any means that have completed chemotherapy and/or trastuzumab will be recruited from the Rowan Breast Center. Up to 18 patients will be enrolled in this Pilot Phase I trial. No exceptions to eligibility will be made.

Fifteen subjects were enrolled at Rowan Breast Center.

Study Schema: Adjuvant HER2+

Inclusion Criteria

- 1. Women ≥ 18 years.
- Subjects with Invasive Breast Cancer at least Stage IIIA ≥ N2 (>4 positive nodes) or have recurrent metastatic breast cancer rendered NED by any means that are classic HER-2 3+ 10%, 2+ IHC and FISH positive or HER-2 2+ FISH negative that have completed chemotherapy and/or trastuzumab and have no evidence of disease.

Version v2 03/01/2017

Pilot Phase I HER-2 Pulsed DC Vaccine to Prevent Recurrence for Patients with HER-2 Driven High Risk Invasive Breast Cancer

- 3. Patients deemed to require anti-estrogen therapy for treatment of their breast cancer can continue anti-estrogen therapy during vaccinations
- 4. Women of childbearing age with a negative pregnancy test documented prior to enrollment.
- 5. Patients with ECOG Performance Status Score of 0 or 1 (Appendix D).

- 6. Women of childbearing potential must agree to use a medically acceptable form of birth control (medically accepted methods: birth control pills, condoms and spermicidal lubricants, intrauterine device, and diaphragm) during their participation in the study.
- 7. Subjects who have voluntarily signed a written Informed Consent in accordance with institutional policies after its contents have been fully explained to them.

Exclusion Criteria

- 1. Pregnant or lactating females.
- 2. Subjects with positive HIV or hepatitis C at baseline
- 3. Subjects with coagulopathies, including thrombocytopenia with platelet count <75,000, INR > 1.5 and partial thromboplastin time > 50 sec
- 4. Subjects with major cardiac illness MUGA < 50% EF.
- 5. Subjects with pre-existing medical illnesses or medications which might interfere with the study as determined by PI.

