6.3 Pre-enrollment screening

- A. Tumor Characteristics
 - 1. A core biopsy or excisional biopsy demonstrating IBC.
 - 2. A standard clinical HER-2/neu immunohistochemical stain and FISH test will be performed using the Hercept test (Dako) on specimens obtained by core biopsy material or resected tumor.
 - 3. A standard clinical ER, PR test.
- B. Baseline patient evaluation
 - 1. All subjects will have a baseline history and physical exam.
 - 2. Laboratory work-up will consist of:
 - a) CBC w/ differential
 - b) PT/PTT
 - c) electrolytes-Na/K/Cl/CO₂/BUN/Cr/glucose
 - d) liver function tests
 - e) urinalysis
 - f) Beta-HCG serum (for all pre and perimenopausal women)
 - g) EKG
 - h) HLA typing (to be obtained as part of study)
 - i) MUGA or Echocardiogram (Must have 50% EF)
 - j) Blood for immune analysis (6 tubes)
 - 3. Baseline radiologic evaluation
 - a) Mammogram up to six months prior to consenting to participate in the study will be acceptable. (Unilateral or bilateral if bilateral mastectomies mammogram not needed)

- b) CT scans of the chest abdomen and pelvis or PET/CT within 60 days of enrollment
- C. Performance of the Pre-screening tests

All of the pre-screening tests will be obtained by the patient prior to first treatment.

1. Histopathologic Testing of Tumor

Subjects will have undergone core or resection of primary tumor prior to enrollment in this protocol to confirm diagnosis of IBC. The Hercept (Dako) antibody will be used to analyze the expression of HER-2/neu on the IBC. Conventional HER-2 3+ 10% of the cells will be considered classic HER-2 positive or 2+ with FISH amplification 2 fold increase in FISH amplicons. For HER-2 2+ FISH negative, ten percent of the cells staining at least 2+ will be considered positive for HER-2/neu expression.

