6.4.6 Administration of the Vaccine

A. Selection of Lymph nodes for vaccination

Ultrasound will be used to identify non-pathologic lymph nodes in the groin as first choice or axilla as second choice. Non-pathologic nodes by ultrasound criteria have a fatty hilum and will

be selected; two nodes per vaccine preferentially 1 node per groin. If a patient has lymphedema or prior groin dissection on a single side then the contralateral groin will be used or alternatively the axilla. Often we only are able to identify 1-2 nodes in the groin by ultrasound. Nodes without a fatty hilum that have evidence of pathologic disease will be excluded from injection.

B. Administration of the initial Vaccine

Vaccines will be labeled (for example, with the subjects study ID, study initials, date and time) prior to release. The patient will be seen by the PI or designee, and Research Coordinator and a history and physical exam will be performed. Ultrasound (US) guided intranodal delivered vaccines will be administered in the NIH Clinical Research Center at Penn or the Clinical Research unit at Moffitt Cancer Center by a radiologist or sonographer experience in ultrasound guidance and the

principal investigators or his/her designee. Each dose will consist of between $1.0-2.0 \times 10^7$ cells and will be injected into 1-2 different normal groin lymph nodes or axillary nodes.

C. Post vaccine assessment

Subjects will be administered the vaccine and observed. All subjects with vaccine related AEs will be followed until the AE has resolved to baseline. Vital signs will be obtained prior to the vaccination and again 15 minutes after the dose is given. Subjects with no noted complications will be then discharged. The anticipated complication could be fever. If an adverse reaction is observed, the subject observation time will be revised appropriately. A physician familiar with the study will be readily available in the event of any complication and such subjects will be transferred to an appropriate care unit for further monitoring and treatment Similarly any discharged subject who develops symptoms will be promptly re-evaluated and admitted for care if inpatient hospitalization is deemed necessary by the principal investigator or his/her designee.

D. Vaccine Schedule

The vaccine schedule is meant to be weekly; however the first 6 vaccines may be given anywhere between 8-21 days apart.

E. Vaccine Tolerance

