Between 8 and 21 days post vaccine the patient will return for the sixth vaccination. Again a history and physical exam will be taken. Any changes in history or physical will be documented. Ultrasound (US) guided intranodal delivered vaccines will be administered in the NIH Clinical Research Center at Penn or the Clinical Research unit at Moffitt Cancer Center by a radiologist or sonographer experience in ultrasound guidance and the principal investigators or his/her designee.

Each dose will consist of between $1.0-2.0 \times 10^7$ cells and will be injected into 1-2 different normal groin lymph nodes or axillary nodes.

O. Post vaccine assessment

Subjects will be administered the vaccines and observed. All subjects with vaccine related AEs will be followed until the AE has resolved to baseline. Vital signs will be obtained prior to the vaccination and again 15 minutes after the dose is given. Subjects with no noted complications will then be discharged. The anticipated complication could be fever. If an Adverse Event is observed, the subject observation time will be revised appropriately. A physician familiar with the study will be readily available in the event of any complication and such subjects will be transferred to an appropriate care unit for further monitoring and treatment. Similarly any discharged subject who develops symptoms will be promptly re-evaluated and admitted for care if inpatient hospitalization is deemed necessary by the PI or his/her designees.

P. Administration of Additional Boost Vaccines.

After the subject has completed 6 vaccines, they will undergo leukapheresis to obtain lymphocyte and monocyte fractions, if needed.

Q. Administration of First Boost Vaccine

Approximately 3 months from completion of the induction vaccines, subjects will receive 3 boost vaccines at approximately 3 month intervals. Again a history and physical exam will be taken. Any changes in history or physical will be documented. Ultrasound (US) guided intranodal delivered vaccines will be administered in the NIH Clinical Research Center at Penn or the Clinical Research unit at Moffitt Cancer Center by a radiologist or sonographer experience in ultrasound guidance and the principal investigators or his/her designee. Each dose will consist of between $1.0-2.0 \times 10^7$ cells and will be injected into 1-2 different normal groin lymph nodes or axillary nodes

R. Post vaccine assessment

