Subjects will be administered the vaccine and observed. All subjects with vaccine related AEs will be followed until the AE has resolved to baseline. Vital signs will be obtained prior to the vaccination and again 15 minutes after the dose is given. Subjects with no noted complications will then be discharged. The anticipated complication could be fever. If an Adverse Event is observed, the subject observation time will be revised appropriately. A physician familiar with the study will be readily available in the event of any complication and such subjects will be transferred to an appropriate care unit for further monitoring and treatment. Similarly any discharged subject who develops symptoms will be promptly re-evaluated and admitted for care if inpatient hospitalization is deemed necessary by the PI or his/her designee.

S. Administration of Second Boost Vaccine

Approximately 3 months from completion of the first boost vaccine Subjects will be administered 2nd boost vaccine. Subjects will first have blood drawn for immune assessment of the boost this will be 5 green top and 1 serum tube. Again a history and physical exam will be

taken. Any changes in history or physical will be documented. Ultrasound (US) guided intranodal delivered vaccines will be administered in the NIH Clinical Research Center at Penn or the Clinical Research unit at Moffitt Cancer Center by a radiologist or sonographer experience in ultrasound guidance and the principal investigators or his/her designee. Each dose will consist of between $1.0-2.0 \times 10^7$ cells and will be injected into 1-2 different normal groin lymph nodes or axillary nodes.

T. Post vaccine assessment

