This vaccine has not been previously administered to individuals who have been treated with Herceptin. Subjects on this trial will have cardiac evaluation of MUGA or echocardiogram to determine their ejection fraction. Subjects will also be closely monitored for signs/symptoms of heart failure. In our first trial there was no evidence of clinically relevant cardiac failure. Less than 8% of subjects had asymptomatic declines in ejection fractions post-vaccine, thought all EFs were still within normal range. There have been no long term cardiac toxicities noted as a result of this vaccine. Additionally, Herceptin does not cause long term cardiac toxicity issues. We do not expect the cardiac toxicity of prior Herceptin treatment and treatment with the vaccine to be additive.

It has been demonstrated that fetuses express HER-2/neu during the third trimester and there is the possibility of spontaneous abortion as a result of anti-HER-2/neu T cell responses against the fetus. Therefore women of childbearing years will be made aware of this possibility.

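### Fetal loss is a named risk, yet pregnancy is tested once, at baseline with no time window, and not again before the other eight of up to nine doses

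*Combined protocol and SAP*

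**What the plan says.** Section 6.2 lists pregnancy as exclusion 1. Inclusion criterion 4 admits "Women of childbearing age with a negative pregnancy test documented prior to enrollment", and criterion 6 requires contraception during participation.

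Sections 6.7.A and 7.0 raise the "possibility of spontaneous abortion as a result of anti-HER-2/neu T cell responses against the fetus". They link it to third-trimester fetal expression of HER-2/neu and say that women of childbearing years will be told.

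The test itself is a serum beta-HCG, item f of the baseline laboratory list in 6.3.B.2. Its timing is set by 6.3.C: "All of the pre-screening tests will be obtained by the patient prior to first treatment". In Appendix 1 the pregnancy test row is marked in the baseline column only.

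On dosing, 6.4.6.D says the schedule is meant to be weekly, "however the first 6 vaccines may be given anywhere between 8-21 days apart". Under 6.4.6.Q, about three months after induction, "subjects will receive 3 boost vaccines at approximately 3 month intervals". Each dosing visit includes a history and physical. The panel in 6.5.B.1, done between induction and the boosts, covers blood count, clotting, electrolytes, liver function, urinalysis and ejection fraction.

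**The concern.** The protocol treats pregnancy as serious enough to exclude, and it names a mechanism by which the vaccine might cause fetal loss. It then checks for pregnancy only before the first dose, although dosing continues for most of a year. A woman who conceives after that check can be vaccinated in early pregnancy with nothing scheduled to show it. Each such dose induces or boosts the T cell response that the protocol gives as the possible cause of harm.

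The baseline test also has no look-back limit. In the same section the CT or PET/CT has 60 days and the mammogram six months. A negative pregnancy test can be out of date within weeks.

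The text available gives no instruction to stop dosing if a subject becomes pregnant. Section 6.7.D takes subjects off protocol for toxicity of grade 3 or above, which is a different matter.

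**Working it through.** **Number of doses.** Section 6.6.B counts nine treatments. This reproduces: 6 induction + 3 boosts = 9, of which 9 − 1 = 8 follow the first. Section 6.9.1 makes the boosts up to three, so nine is a maximum.

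**Timing of doses.** Inputs are the 8 to 21 day gaps (6.4.6.D; five gaps between six vaccines) and about 3 months, taken as 91 days, before each boost (6.4.6.Q, S and U).

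| Dose | Days after vaccine 1 |
|---|---|
| Vaccine 6 | 5 × 8 = 40 to 5 × 21 = 105 |
| Boost 1 | add 91: 131 to 196 |
| Boost 2 | add 182: 222 to 287 |
| Boost 3 | add 273: 313 to 378 |

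In months the last dose is at 313 / 30.4 = 10.3 to 378 / 30.4 = 12.4. The interval from the test is longer still, by an amount the protocol does not limit.

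**Where the exposure lies.** The three long gaps total 3 × 91 = 273 days, which is 273 / 378 = 72% to 273 / 313 = 87% of the dosing period. A pregnancy begun within one gap is at most 91 / 7 = 13 weeks from conception at the next boost. A history and physical may miss a pregnancy at that stage.

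**Which tests are repeated.** Comparing 6.3.B.2 with 6.5.B.1, baseline items a to e and the ejection fraction study reappear before the boosts. Beta-HCG, item f, does not. These prose lists agree with Appendix 1, so the gap is not an artefact of how the table was extracted.

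**Whether third-trimester expression confines the risk.** Section 5.3 reports later blood samples from 17 of 27 subjects, taken 8 to 48 months after a four-dose series without boosts: "All subjects showed long-term CD4 T cell immunity to vaccine peptides by ELISpot". A response raised or boosted early in pregnancy could therefore still be present in the third trimester.

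**Expected number of pregnancies.** The documents do not give the number of pre- or perimenopausal women. I assume 4 to 10 of 18 and a yearly pregnancy rate of 1% to 10%.

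- Low: 4 × 0.01 × 313 / 365 = 0.03
- High: 10 × 0.10 × 378 / 365 = 1.04

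Fifteen subjects were already enrolled. Scaled to the remaining 18 − 15 = 3, the range is 0.03 × 3 / 18 = 0.005 to 1.04 × 3 / 18 = 0.17, plus an unknown contribution from enrolled women with boosts outstanding.

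**Effect of retesting.** With a test just before vaccine 1 and before each boost, the longest interval from test to dose falls from 313–378 days or more to at most 105 days (vaccine 6 on the slowest schedule) plus the stated window.

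**The case against.** The protocol does not rely on one test alone. It requires contraception throughout, warns women, takes a history and physical at every dose, and in 6.5.B.1 lets the investigator bring laboratory work forward for abnormal symptoms. Together these would probably reveal an advanced pregnancy. They would not reliably reveal an early one before a boost, and no later check on contraception is scheduled.

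The hazard is described only for the third trimester, and the persistence data come from a different group: volunteers from a DCIS trial given four vaccines, none of whom had just had chemotherapy or trastuzumab. If immunity does persist, withholding a boost removes only an increment of risk, of unknown size. That limits the benefit, but stopping further doses and allowing counselling and monitoring still has value.

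Pregnancies will be few, the frequency inputs are assumed, and most subjects were already enrolled. This stands; the case does not depend on frequency.

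Reuse of samples is not assured. The urinalysis before the boosts has no fixed day and might fall outside a 7-day window, and the boost blood is allocated to immune assays. A separate test may be needed.

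No other baseline laboratory test has a day window either. That is so, but a negative pregnancy result dates quickly.

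**Conclusion.** The concern holds. Followed as written, the plan allows further vaccination in an unrecognised early pregnancy, because up to eight doses over about 10 to 12 months are given with no repeat test and the baseline test has no maximum age. The boosts matter most, since the gaps before them make up 72–87% of the dosing period.

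The expected number of pregnancies is small: 0.03 to 1.0 across 18 subjects if 4 to 10 could conceive at 1% to 10% a year, and fewer among those still to be enrolled. No endpoint, stopping boundary or analysis is affected. The change is recommended because the harm is serious and named in the protocol, and the remedy is cheap.

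**What to change.** Amend 6.3, 6.5.B.1 and Appendix 1 to require, in pre- and perimenopausal women, a negative pregnancy test within a short stated window (for example 7 days) before vaccine 1 and again before each of boosts 1, 2 and 3. The result should be known before the dose is given. State that dosing stops if a test is positive, and that the woman is counselled and monitored. Say openly that vaccines 2 to 6 continue to rely on contraception, history and physical, and that this residual risk is accepted.

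The cost is a schedule amendment and up to three inexpensive tests per woman concerned. Where timing allows, these can use the urine taken for the Booster 1 urinalysis or the blood already drawn before the boosts; for boost 2, 6.4.6.S says "Subjects will first have blood drawn for immune assessment of the boost". The downside is an occasional delayed or discarded dose, since 6.4.3 allows prepared vaccine to be kept only 4 to 6 hours. Testing before the vaccine is made or thawed would avoid most of that waste. The change reaches the remaining enrolments and any enrolled woman with boosts outstanding; re-consent at the second site is a natural point to introduce it.
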